5.1.4 Baseline Assessment - Neuropsychological Outcome Measures

Within one month of enrollment and before initiation of treatment, participants will be administered all primary and secondary outcome measures as outlined in section 5.1.4.1. The child's history will also be reviewed with the family to gather information about the child's cognitive development and behavior.

5.1.4.1 Primary Outcome Measures

The effect of Lovastatin on cognitive functioning in children with NF1 has not been examined. Evidence from a murine model of NF1 suggests Lovastatin improves visual spatial learning and memory, and attention. As such, the following primary outcome measures are:

- Visual Spatial Learning and Memory

*CANTAB Paired Associate Learning (PAL)

PAL is a measure of arbitrary visuospatial associations. It involves the randomized „opening“ of six boxes that are displayed on the screen, each revealing a different pattern. Immediately after presentation of the six patterns, each item reappears in the central box in random order and the participant has to indicate where each item was first seen. Measures include the number of patterns placed correctly on the first trial and the number of repeat presentations needed to learn all the associations correctly. Administration time for this measure is approximately 10 minutes.

- Attention

*Score! Subtest from the Test of Everyday Attention for Children (TEA-Ch: Manly, Robertson, Anderson & Nimmo-Smith, 1999).

The TEA-Ch is a normed and standardized multi-subtest battery that assesses various aspects of attentional function in children aged between 6 years and 15 years 11 months. The Score! subtest requires children to keep count of sounds they hear on a tape. This task does little to „grab“ the child's attention and is a measure of their ability to self-sustain his or her own attention. Previous findings indicate that approximately 63% of children with NF1 are impaired on Score! (Hyman et al., 2005). There are two alternate forms for this subtest and it takes approximately 8 minutes to complete.

5.1.4.2 Secondary Outcome Measures

- Attention

*Test of Everyday Attention for Children (TEA-Ch: Manly et al., 1999)

In addition to the Score! subtest, three other subtests from the TEA-Ch will also be used in this study: Sky Search (visual selective attention), Sky Search Dual Task (divided attention between visual and auditory information), and Creature Counting (attentional control/switching). The test is normed for children 6 to 15 years 11 months and there are two alternate forms available. Administration time for these three subtests is approximately 20 minutes.

*Conners' Continuous Performance Task – II (CPT-II: Conners, 2000)

CPT-II is a computerized measure of sustained attention and concentration. It is a 14-minute computerized test that requires the child to discriminate targets (X's) from nontargets (letters of the alphabet). Various measures calculated by the program include hit reaction time, omission and commission errors, change in reaction time speed and consistency. This test takes approximately 14 minutes to administer.

Parent version of the Conners ADHD/DSM-IV Scales (CADS: Conners, 1997)

The CADS-P is a published questionnaire that uses observer ratings to help assess the presence of inattentive and hyperactive/impulsive behaviors in children and adolescents and directly corresponds to the DSM-IV criteria for ADHD. The parent version of the questionnaire will be administered, which contains 26 items (12 items ADHD index, 9 inattentive items and 9 hyperactive-impulsive items). It takes approximately 5 to 10 minutes to complete. The CADS-P is a subjective outcome measure of attention.

- Executive Functions

*CANTAB Spatial Working Memory (SWM)

This is a test of the participant's ability to retain spatial information and to manipulate remembered items in working memory. It is a self-ordered task that also assesses heuristic strategy. Administration time for this test is approximately 10 minutes.

*CANTAB Stockings of Cambridge (SOC)

This is a test of spatial planning and problem solving (aspect of executive function), which is based on the „Tower of London“ test (Shallice, 1982). Administration time for this measure is approximately 10 minutes.

*CANTAB Stop Signal Task (SST)

This is a classic stop signal response inhibition test that uses interleaved staircase functions to generate an estimate of stop signal reaction time. SST gives a measure of the participant's ability to inhibit a response. Administration time for this task is approximately 15 minutes.

Controlled Oral Word Association Test (COWAT; Benton & Hamsher, 1989)

The COWAT assesses the executive aspects of language processing, including verbal fluency and concept formation. It requires children to rapidly make verbal associations to specific letters of the alphabet (i.e., F, A and S). The test is normed for children between 7 to 16 years of age (Anderson, Lajoie & Bell, 1995). Administration time for the COWAT is approximately 5 minutes.

Behavior Rating Inventory of Executive Function-Parent - Report Form (BRIEF; Gioia, Isquith, Guy & Kenworthy, 2000; Guy, Isquith & Gioia, 2004)

The BRIEF is a published clinical questionnaire assessing executive function in the home and school setting. The Parent Form is completed by the child's parent or guardian. It contains 86 items, with eight clinical scales and two validity scales. Behavior descriptors of a child are rated on a three-point Likert scale: "never," "sometimes," "always." Items were developed to capture everyday behaviors associated with executive functions, and tap eight domains including: initiate, inhibit, shift, plan, organize, self-monitor, emotional control, and working memory. These scales are combined to form two broader indices (Behavioral Regulation and Metacognition) and a Global Executive Composite score. The Parent Form is normed for parents of children aged 5-18 years old. This questionnaire takes approximately 15 minutes to complete.

- Visual Spatial Skills

*Judgment of Line Orientation (JLO: Benton, Varney & Hamsher, 1976)

The JLO is a motor-free untimed measure of spatial perception and orientation. JLO requires participants to judge the spatial directionality and size of angles. Two alternative forms of this test are available. These tests take approximately 10 minutes to administer.

- Visual Perceptual Skills

Object Assembly (Wechsler Scale for Intelligence – Third Edition; WISC-III; Wechsler, 1991)

The Object Assembly test is a perceptual organization timed task, that is, a task that requires mentally organizing spatial information into meaningful part-whole relationships. For this task, participants are required to put together puzzle pieces to form line drawings of common objects. This test takes approximately 13 minutes to complete.

- Behavior

Behavior Assessment System for Children - Second Edition (BASC-II; Reynolds & Kamphaus, 2004)

The BASC-II is a multidimensional system used to evaluate the behavior and self-perceptions of children and young adults aged two through 25 years. The Parent Rating Scales is a comprehensive measure of the child's adaptive and problem behaviors in community and home settings, which takes 10 to 20 minutes to complete. It assesses various internalizing and externalizing problem behaviors as well as adaptive skills. The Self-Report of Personality is a personality inventory for children and adolescents, and young adults, which takes about 30 minutes to complete. It assesses various internalizing problems, hyperactivity/inattention, personal adjustment and school problems.

- Quality of Life

The Pediatric Quality of Life Scale (PedsQL: Varni, Seid & Kurtin, 2001)

The PedsQL 4.0 Generic Core Scales are multidimensional child self-report and parent proxy-report scales to assess health-related quality of life in children and adolescents aged 2 to 18 years. There are parallel child and parent scales, which include self-report forms for children,

and proxy-report forms for parents. The PedsQL consists of four core scales: physical, emotional, social, and school. It takes 5 to 10 minutes to complete.

- Visuospatial Learning and Memory

Computer Generated Arena (CGA: Astur, Taylor Mamelak, Philpott & Sutherland, 2002)

The CGA is an optional computerized clinical outcome measure that will be performed after completion of all secondary outcome measures. It is a virtual environment task that has been developed as a “Human Morris Water Maze” (Astur et al., 2002; Kallai, Makany, Karadi & Jacobs, 2005). The task requires children to use a joystick controller to navigate a circular “arena” to locate an invisible target hidden on the floor. The walls of the arena contain cues, such as windows that remain in place. The fixed target must be located in subsequent trials, each time starting from a new location. This test takes 10-15 minutes to administer and will only be conducted at the following sites: The Children’s Hospital at Westmead, Children’s Hospital Boston and Children’s National Medical Center.

In addition to these measures, Motor Screening (MOT) from the CANTAB will also be administered. MOT is a simple pointing task that measures psychomotor speed and introduces the participant to the touch-screen apparatus, ensuring they can touch the screen accurately, and can hear, understand and follow instructions. The mean latency to touch a cross is measured. MOT takes approximately 5 minutes to administer.

All primary measures will be administered at screening. The length of time required for the child to complete the remainder of the baseline neuropsychological assessment is estimated to be 128 minutes (98 minutes testing and 30 minutes to complete self-report questionnaires). It is estimated that parent questionnaires will take 55 minutes to complete (see Appendix 5). All neuropsychological assessments that will be used in this study are published tests that have normative data that is both reliable and valid for the age range in this study. These tests are all extensively used in clinical and/or research settings. All tests have standardized instructions for administration ensuring there will be no site variation in administration.

To minimize any test-retest effects for neuropsychological outcome measures, alternate forms (indicated by „*“ in the above sections 5.1.4.1 and 5.1.4.2) will be used where possible, to minimize potential practice effects. Furthermore, the use of a placebo group will allow us to identify any potential practice effects and distinguish whether any changes in the treatment group are larger than those accounted by practice effects i.e. a treatment effect. In addition, statistical analysis of the data will be conducted to account for confounding variables such as practice effects (see Section 8).

5.1.5 Randomization

Following a successful screening period, the participant will be randomized to one of the two treatment groups: Lovastatin or placebo. Randomization will be implemented by the Data Coordinating Center for this trial utilizing a permuted blocks approach.

Randomization will be stratified by clinical site, to ensure adequate balance between the treatment groups, overall and at each site. Password protection will be implemented to ensure that only certified clinical center personnel are allowed to randomize patients and access the database. At the time of randomization, each participant will be assigned a unique medication kit identification number that will be used throughout the duration of the study.

5.1.6 Masking Procedure and Labeling

In order to preserve the double-masking of the trial, only the Data Coordinating Center, the drug distribution center, and the pharmacist at each participating site will be unmasked. The drug distribution center will be provided with the randomization sequence and treatment assignment directly by the Data Coordinating Center.

Both treatments (Lovastatin and placebo) will be distributed from the Pharmacy Department at each site. Except for the pharmacist, all staff will be blinded to the treatment sequence at each site.

The success of blinding will not be evaluated. While the CONSORT checklist previously stated that the success of blinding should be evaluated this statement has recently been removed from the CONSORT checklist as it was deemed that testing for blindness may not generate valid answers (Sackett, 2007).

5.2 Treatment Visits

5.2.1 Dose Schedule and Prescription

Eligible participants will be dispensed 20mg of Lovastatin or the placebo at the initiation of treatment. Participants will be given directions to take the medication once daily after dinner time. Given that Lovastatin has a strong odor; participants will be required to swallow the capsule whole without breaking the seal. Participants will take one tablet (20mg Lovastatin) per dose for two weeks; and increase to two tablets per dose during the following weeks (40 mg Lovastatin). Participants will continue on the same dosage for a total of 14 weeks. In order to assess medication compliance, participants will be required to complete pill diary forms. All participants will be provided with a complete list of medications and products that have detrimental interactions with Lovastatin that must be completely avoided while being treated with Lovastatin (see Appendix 6).

5.2.2 Clinical Evaluation

Throughout the treatment phase of the study, participants will be clinically evaluated every 4 weeks (\pm 4 days) by a neurologist or a qualified physician at each site. At each visit, an interim medical history and physical examination (including a neurological examination) will be performed. Height, weight and body surface area will be obtained. Participants will be assessed for toxicity/side effects and safety labs will be performed as specified in section 5.1.3 every 4 weeks (\pm 4 days). Medication compliance will also be assessed at these visits. Pill diaries will be

reviewed and a pill count will be performed and recorded. At the end of the study or the treatment period, all unused medication will be collected and disposed of properly on a per site basis according to clinical procedures and guidelines.

5.2.3 Off-Study Criteria (Note: See Section 6.6 for modifications for toxicity information)

A participant will be taken off the study for the following reasons:

- The participant refuses further treatments and/or wishes to withdraw from the study;
- For participants concurrently taking stimulant medications (methylphenidate and/or dextroamphetamines), they will be withdrawn from the study if they stop or change the dose or type of stimulant medication before their final study visit;
- It is deemed in the best interest of the participant to stop the study by the research team;
- Serious protocol violation or non-compliance as determined by the principal investigator or research team;
- The development of significant drug toxicity, such as recurrent grade 3 or 4 toxicity after dose reduction; and/or persistent grade ≥ 2 toxicity for >10 days without administration of the drug;
- The development of a concurrent serious medical condition that might preclude or contraindicate the administration of Lovastatin;
- Death.

5.3 Post-Treatment

The following tests and procedures will be performed at the end of the 16-week treatment period (unless participants have come off treatment early):

- Medical history and physical examination;
- Laboratory studies as specified in section 5.1.3 including CBC, BUN, creatinine, ALT, AST, direct and total bilirubin, CPK and complete lipid profile;
- All outcome measures will be re-administered 16 weeks (± 4 days) after treatment commenced (and the day it is terminated). In exceptional situations where participants are unable to attend the post-treatment assessment at week 16 (± 4 days), the post-treatment assessment will be conducted earlier, but as close to week 16 as possible. If a participant is withdrawn from the study early, the battery will still be given, if it is at least four weeks since the baseline assessment (unless the reason is non-compliance of medication). It is estimated that it will take the child approximately 148 minutes (118 minutes testing and 30 minutes self-report questionnaires) to complete the primary and secondary outcome measures. It is estimated that parent questionnaires will take 55 minutes to complete.

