5.4 Follow-up

To determine any carry-over effects in the present study, a follow-up assessment will be conducted 8 weeks (± 7 days) post cessation of treatment. As treatment status will be blinded, all participants will be re-administered all outcome measures and laboratory tests (excluding pregnancy test) at follow-up. While no existing data exist on the carry-over effects of Lovastatin, in patients with cancer who were given high dosages of Lovastatin (2-45mg/kg/day)

approximately 30 days after the cessation of Lovastatin, cholesterol levels returned back to normal levels (Thibault et al., 1996).

All study personnel that have responsibility for direct participant related activities will be intensively trained in the relevant specific procedures before contact with participants, which includes providing informed consent/assent, family/child interviews, the administration and scoring of tests, maintenance of confidentiality, data collection and handling, and procedures for handling difficulties that might arise during the study. All study personnel who have direct contact with study participants or their data, will sign a confidentiality form, indicating their understanding of appropriate procedures for maintaining participant confidentiality. Doctoral-level neuropsychology staff and physicians will provide the relevant training and ongoing supervision of all study personnel.

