7.0 Statistics

Determination of sample size: No data exist on the effects of Lovastatin in children with NF1. A clinical and meaningful difference for primary efficacy measures is defined as an effect size of one half of a standard deviation, which is classified as a treatment effect of medium magnitude (Cohen, 1988). A sample size of 64 participants per treatment group (128 total) will be sufficient to detect an effect size of half a standard deviation at the two-sided 0.05 significance level with power of 0.80 (Peat, Mellis, Williams & Xuan, 2001). To allow for a 10% dropout rate prior to the 16-week point, a total of 142 participants will be enrolled.

Interim analyses: Interim analyses will be done under the purview of the DSMB, which will set the content and frequency of analyses. We will propose a Charter containing a data monitoring plan that will include stopping guidelines. We expect these to be the Lan DeMets modifications of the O'Brien Fleming boundaries (Lan & DeMets, 1983; O'Brien & Fleming, 1979)). It is expected that the DSMB will review this charter during its first meeting.

Data analysis: Demographic and baseline characteristics will be summarized for each group using descriptive statistics. Intention-to-treat analyses will be conducted for the primary outcomes measures. An intention-to-treat analysis provides an unbiased, conservative and consistent estimate of a treatment effect (Heritier, Gebiski & Keech, 2003).

Analyzing change scores from baseline to post-treatment does not control for baseline imbalance because of the regression to the mean (Vickers & Altman, 2001). Also, with changes scores, if the treatment is effective, the statistical significance of the treatment effect will depend upon the correlation between baseline and follow-up scores. Therefore, to determine whether there has been a significant change from baseline to post-treatment, primary and secondary outcomes will be analyzed using ANCOVA, which is a better approach than analyzing change scores with independent t-tests (Vickers & Altman, 2001).

In addition, at an individual case level to determine whether test-retest change scores from baseline to post-treatment are reliable and clinically meaningful, standardized regression based

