7.0 Statistics

Determination of sample size: No data exist on the effects of Lovastatin in children with NF1. A clinical and meaningful difference for primary efficacy measures is defined as an effect size of one half of a standard deviation, which is classified as a treatment effect of medium magnitude (Cohen, 1988). A sample size of 64 participants per treatment group (128 total) will be sufficient to detect an effect size of half a standard deviation at the two-sided 0.05 significance level with power of 0.80 (Peat, Mellis, Williams & Xuan, 2001). To allow for a 10% dropout rate prior to the 16-week point, a total of 142 participants will be enrolled.

Interim analyses: Interim analyses will be done under the purview of the DSMB, which will set the content and frequency of analyses. We will propose a Charter containing a data monitoring plan that will include stopping guidelines. We expect these to be the Lan DeMets modifications of the O'Brien Fleming boundaries (Lan & DeMets, 1983; O'Brien & Fleming, 1979)). It is expected that the DSMB will review this charter during its first meeting.

Data analysis: Demographic and baseline characteristics will be summarized for each group using descriptive statistics. Intention-to-treat analyses will be conducted for the primary outcomes measures. An intention-to-treat analysis provides an unbiased, conservative and consistent estimate of a treatment effect (Heritier, Gebiski & Keech, 2003).

Analyzing change scores from baseline to post-treatment does not control for baseline imbalance because of the regression to the mean (Vickers & Altman, 2001). Also, with changes scores, if the treatment is effective, the statistical significance of the treatment effect will depend upon the correlation between baseline and follow-up scores. Therefore, to determine whether there has been a significant change from baseline to post-treatment, primary and secondary outcomes will be analyzed using ANCOVA, which is a better approach than analyzing change scores with independent t-tests (Vickers & Altman, 2001).

In addition, at an individual case level to determine whether test-retest change scores from baseline to post-treatment are reliable and clinically meaningful, standardized regression based

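### Section 5.3 withholds the post-treatment battery from children withdrawn for non-compliance (and from very early withdrawals), which conflicts with the intention-to-treat commitment for the primary outcomes

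*Protocol*

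**What the plan says.** Section 7.0, worded alike in the Protocol and the SAP, states: "Intention-to-treat analyses will be conducted for the primary outcomes measures". The primary analysis is ANCOVA of post-treatment scores. Mixed models are optional and are offered to describe change over time. Neither document defines the intention-to-treat set, names a missing-data method or plans a missing-data sensitivity analysis. The only allowance for loss is in the sample size: "To allow for a 10% dropout rate prior to the 16-week point, a total of 142 participants will be enrolled".

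Protocol section 5.3 lists the end-of-treatment procedures but excepts children who came off treatment early. For those withdrawn early, "the battery will still be given, if it is at least four weeks since the baseline assessment (unless the reason is non-compliance of medication").

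Section 5.2.3 gives as one reason for being taken off study: "Serious protocol violation or non-compliance as determined by the principal investigator or research team". Section 5.2.2, on the four-weekly visits, says: "Medication compliance will also be assessed at these visits". Appendix 3 adds a compliance check at week 2. No pill-count threshold is stated.

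Two further timing rules matter. For exceptional cases who cannot attend at week 16, section 5.3 says "the post-treatment assessment will be conducted earlier, but as close to week 16 as possible", with no earliest date. Section 5.4 says "a follow-up assessment will be conducted 8 weeks (± 7 days) post cessation of treatment" and that "all participants will be re-administered all outcome measures and laboratory tests (excluding pregnancy test) at follow-up".

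**The concern.** Intention-to-treat exists so that adherence after randomisation does not decide who is analysed. Here the protocol itself stops collection of the primary outcome in a group defined by adherence, and the investigator or research team decides who belongs to it. The four-week floor does the same for very early leavers and is the lesser route.

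The primary ANCOVA would then run on a set selected after randomisation. Non-compliant children may plausibly differ in outcome even after baseline adjustment, and the scores that were collected cannot show whether they do. The sample-size inflation protects power, not validity.

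The sections also leave gaps around the rule. Section 5.3 gives no date for the battery in withdrawn children and does not say whether it stands as the week-16 score. Section 5.4 tests all participants but does not say whether that includes children taken off study under section 5.2.3.

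**Working it through.** **The plan's own figure.** Inputs from section 7.0: 0.5 SD, two-sided 0.05, power 0.80. The two-sample t-test needs 63.8, so 64 per arm (power 0.801). 128/0.9 = 142.2 against 142 enrolled. The figure reproduces, and planned dropout is 142 − 128 = 14. A loss of 10% leaves power at 0.80, so the issue is bias, not sample size.

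**When bias arises.** Complete-case ANCOVA was simulated with no true effect, 1,000,000 per arm and assumed baseline correlations of 0.5 and 0.7.
- Missingness driven by arm and baseline only (7.0% v 2.8%, 10% v 5%, 15% v 5%): ANCOVA bias is about 0.002 SD or less, while the raw mean difference is off by 0.02 to 0.06 SD.
- Missingness driven by the residual (7.0% v 2.8%, deficit about 1 residual SD): ANCOVA bias is about 0.04 residual SD.

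**Size.** Shift = residual deficit of untested children × (untested share active − untested share placebo). Type I error is the two-sided noncentral-t rejection rate at 64 per arm, 125 df, with no true effect. The documents give no count of untested children, so every split and deficit is an assumption. SD means residual SD after baseline adjustment.

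| Untested, active v placebo | Difference in share | Shift at 0.5 / 1 SD | Type I error |
|---|---|---|---|
| Equal rates and deficits | 0 | 0 / 0 | 0.050 |
| 4 v 3 of 71 (half of 14) | 1/71 = 0.014 | 0.007 / 0.014 | 0.0502 / 0.0507 |
| 5 v 2 of 71 (half of 14) | 3/71 = 0.042 | 0.021 / 0.042 | 0.0516 / 0.0564 |
| 15% v 5% (about all 14) | 0.10 | 0.05 / 0.10 | 0.0591 / 0.0868 |

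The table takes more untested children on lovastatin and worse scores among them, which favours lovastatin. Reversing either assumption reverses the shift.

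**Reach of the four-week floor.** It runs from baseline, not first dose. If the gap from baseline to first dose is 0, 2 or 4 weeks (assumed), the floor excludes leavers in the first 4, 2 or 0 weeks on drug. Section 5.1.3 puts the enrolment laboratory test at least two weeks before dosing. If the primary measures taken at screening share that visit and serve as baseline, the floor reaches at most the first two weeks. Section 5.1.4 describes a baseline assessment within one month of enrolment, so the gap is not settled.

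**Sections 5.3 and 5.4 together.** For a child who stops at week 8, the visit 8 weeks after cessation falls at week 16. For one who stops at week 9 or 10, it falls at week 17 or 18.

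**Dilution once untested children are tested.** If 5%, 7% or 10% of the active arm carry no effect, the contrast is 0.5 × 0.95, 0.93 or 0.90 = 0.475, 0.465 or 0.45 SD. Power is 0.80, 0.79 or 0.76 at 71 per arm (nobody missing). With 5% still missing (71 × 0.95 = about 67.5 per arm) it is 0.78, 0.76 or 0.74. Reaching 0.80 needs 71, 74 or 79 per arm.

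**The case against.** The strongest reply is that the effect is probably small. Sites are blinded. The phase I children tolerated the drug well, and the trial in adolescent boys with familial hypercholesterolaemia found similar side-effect profiles in the two arms (sections 1.4 and 1.5). The withdrawal reasons most likely to differ by arm, such as toxicity, are separate categories in section 5.2.3 and still lead to a battery once four weeks have passed. That stands: near-equal rates are plausible, and a reader should not infer that the trial is seriously biased, or biased towards lovastatin.

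A second reply is that section 5.4 already tests everyone. Its wording does not settle whether children taken off study are included, and an off-drug visit timed from cessation is not the week-16 endpoint except for a child who stops near week 8.

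Three stronger readings are tempting but not supported:
- That withdrawn children are tested on the day they leave. Section 5.3 sets no date.
- That week 16 is already a scheduled visit for these children. They are off study under section 5.2.3, and section 5.3 excepts them from the end-of-treatment procedures, so it would be an added visit.
- That a mixed model or multiple imputation would cure the problem. With only arm and baseline to work from, either gives essentially the complete-case ANCOVA answer and leaves bias from outcome-related missingness in place.

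Intention-to-treat is also not wholly abandoned: children who are tested can still be analysed by assigned arm.

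**Conclusion.** The concern holds as a faulty rule, not merely missing detail: followed as written, section 5.3 selects the primary analysis set partly on adherence after randomisation, against the commitment in section 7.0. The non-compliance exclusion is the main defect and the four-week floor the lesser one. Bias depends on missingness being related to outcome beyond arm and baseline, and on rates or deficits differing between arms. Under modest assumed imbalance, type I error is 0.050 to 0.056. The 0.087 figure needs all 14 planned dropouts untested, split 15% v 5%, each 1 residual SD worse. Direction is unknown. It should be fixed because the rule defeats its own stated principle and the change is cheap, not because a large error has been shown.

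**What to change.** **Section 5.3.** Delete the non-compliance exception and the four-week floor. State that every randomised child is invited to the week-16 battery whether or not study drug has stopped, unless consent or assent is withdrawn. State the earliest date at which an exceptional test counts as week 16. Leave all drug-stopping and safety rules unchanged.

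**Sections 5.2.3, 5.3 and 5.4.** Reconcile whether children taken off study are tested. For early stoppers, give the week-16 battery priority and do not repeat the section 5.4 cognitive battery where it would fall within a few weeks of it. The laboratory and safety parts of that visit stay as they are. This avoids two sessions a week or two apart on Score!, which has only two alternate forms.

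**Section 7.0.** Analyse all randomised children by assigned arm and name the method for scores still missing. State that a battery given well before week 16 is not relabelled as week 16. Add a sensitivity analysis that worsens untested children's scores by, for example, 0.5 and 1 residual SD. Define worsening in the direction of impairment for each measure, because one Paired Associate Learning measure counts repeat presentations and a lower count is better. The gain comes from collecting the scores and from this sensitivity analysis, not from the choice of model.

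**Cost.** Amendment wording plus roughly 7 to 14 added week-16 sessions (half or all of planned dropout), or up to about 28 if section 5.4 does not now cover these children. At 148 child minutes each, 7 × 148 = 17 hours and 28 × 148 = 69 hours, plus 55 parent minutes per session. Some families will decline, some carry-over data are lost for early stoppers, and the effect may be diluted as shown in the power figures above.
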